8.1.2.1 Response Rate (RR)

Response rate is defined using the RECISTv1.1 criteria as the proportion of subjects with a confirmed CR or confirmed PR. The point estimate of the RR with a 95% confidence interval based on the exact binomial distribution will be evaluated.

8.1.2.2 Overall Survival (OS)

Overall survival will be defined as the time from administration of the initial dose of cabozantinib until death from any cause. PFS is defined above. Kaplan-Meier estimates of overall survival and progression-free survival rates will be calculated along with their corresponding 95% confidence interval.

8.1.2.3 Tolerability and Safety

For the safety analysis, all enrolled patients who receive at least one dose of cabozantinib will have information collected on adverse events, which will be summarized by dose and severity as assessed by the Common Toxicity Criteria for Adverse Events (CTCAE), v.4.0 and relationship to cabozantinib.

8.1.2.4 PFS and RR Based on Molecular Status

Analysis of the PFS and RR in patients based on RAS, BRAF, and PIK3CA mutation status will be done with point estimates of 95% confidence intervals provided for each group, and comparisons will be made using a stratified log-rank test. Other biomarkers may be evaluated based on ongoing preclinical experiments as well as the scientific literature.

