Adverse event seriousness, severity grade, and relationship to study treatment will be assessed by the investigator. Severity grade will be defined by the National Cancer Institute (NCI) Common Terminology Criteria for Adverse Events (CTCAE) version 4.0.

TUMOR ASSESSMENTS

Tumors will be assessed by CT or MRI methods at a frequency of every 6 weeks for the first 12 weeks, then every 9 weeks thereafter.

BIOMARKER ASSESSMENTS

Whole blood samples will be obtained pretreatment and +/- 5 days of Cycle 3 Day 1 from consenting patients, which will then be shipped and stored in a repository for future analysis at The University of Arizona. Pending funding availability, archival tumor specimens will be genotyped at The University of Arizona Genetics Core, a CLIA-certified clinical laboratory. Other biomarkers may be evaluated based on ongoing preclinical experiments as well as the scientific literature.

OTHER ASSESSMENTS

Pending funding availability, MET copy number analysis and expression will be assessed by fluorescent in situ hybridization (FISH) and immunohistochemistry (IHC), to explore association with likelihood of response and/or PFS at 12 weeks in patients with metastatic refractory colorectal cancer treated with cabozantinib. Other biomarkers may be evaluated based on ongoing preclinical experiments as well as the scientific literature.

STATISTICAL METHODS

1. Definition of primary outcome/endpoint:
 - a) PFS will be defined as the time from administration of the initial dose of cabozantinib to evidence of radiographic progression as defined by RECIST criteria or death from any cause without evidence of disease progression, whichever occurs first.
2. Definition of secondary outcomes/endpoints:
 - a) RR is defined using the RECIST 1.1 criteria as the proportion of subjects with a confirmed CR or confirmed PR.
 - b) OS will be defined as the time from administration of the initial dose of cabozantinib until death from any cause.
 - c) Safety and tolerability analysis of cabozantinib summarized by dose and severity as assessed by the Common Toxicity Criteria for Adverse Events (CTCAE) version 4.0 and relationship to study drug.
 - d) Retrospective analysis of the PFS and RR in patients based on RAS, BRAF, and PIK3CA mutation status through a separate analysis analyzing RR and PFS by RAS, BRAF, and PIK3CA mutation status to those without such mutations.
3. Definition of exploratory outcomes/endpoints:

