 - a) Exploratory analysis of predictive and pharmacodynamic markers by obtaining pre- and post-treatment whole blood samples pretreatment and +/- 5 days of Cycle 3 Day 1 of treatment for each patient and archived for future studies and analysis.
4. Analytic plan for primary objective:
 - a) PFS – each patient will be examined for PFS at 12 weeks and dichotomized as either having progression or not. Using an optimal Simon 2-stage design the first 16 patients will be enrolled and 12-week PFS will be determined. Study enrollment will continue after the 16th patient is accrued and dosed, and at least 3 patients have met the 12 week PFS time point. If 3 or more of these patients have not progressed by 12 weeks, the trial will accrue an additional 28 patients for a total of 44 patients. If 10 or more (total) of these 44 patients are free of progression at 12 weeks, then the Null Hypothesis will be rejected in favor of the alternative suggesting that the treatment has sufficient efficacy to warrant future study.
 - i. PFS – Kaplan-Meier estimates of progression-free survival rates will also be calculated along with their corresponding 95% confidence intervals.
5. Analytic plan for secondary objectives:
 - a) RR - defined using the RECIST criteria as the proportion of subjects with a confirmed CR or confirmed PR. The point estimate of the RR with a 95% confidence interval based on the exact binomial distribution will be presented.
 - b) OS – Kaplan-Meier estimates of progression-free survival rates will be calculated along with their corresponding 95% confidence intervals.
 - c) Safety and tolerability analysis - all enrolled patients who receive at least one dose of cabozantinib will have information collected on adverse events, which will be summarized by dose and severity as assessed by the Common Toxicity Criteria for Adverse Events (CTCAE) v. 4.0 and relationship to Study Drug.
 - d) Retrospective analysis of the PFS and RR in patients based on RAS, BRAF, and PIK3CA mutation status - point estimates with 95% confidence intervals will be provided for each group, and comparisons will be made using a stratified log-rank test.

6. Analytic plan for exploratory analysis:
 - a) Exploratory analysis – peripheral blood collections pretreatment and +/- 5 days of Cycle 3 Day 1 will be obtained and archived for future investigation of predictive and pharmacodynamics biomarkers.
7. Sample size justification:

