2 STUDY OBJECTIVES AND DESIGN

2.1 Study Objectives

The objectives of this study are as follows:

Primary Objective:

- 1) To determine the clinical activity of cabozantinib in patients with refractory metastatic CRC using progression free survival (PFS) as primary endpoint.

Secondary Objectives:

- 1) To determine the response rate (RR) in patients with refractory metastatic CRC treated with cabozantinib.
- 2) To determine the overall survival (OS) in patients with refractory metastatic CRC treated with cabozantinib.
- 3) To describe safety and tolerability of cabozantinib in this group of heavily pretreated patients.
- 4) To retrospectively explore the PFS and RR in patients based on RAS, BRAF, and PIK3CA mutation status.

Exploratory Objectives:

- 1) Exploratory analysis of predictive and pharmacodynamic markers.

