2.4 Blinding and randomization

This is an open-label, single-arm study which requires no blinding or randomization.

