7.3 Sample Size

The stage I sample size will consist of 16 subjects for interim analysis, then an additional 28 subjects for stage II for a total of 44 subjects.

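### The log-rank test named for comparing response rate by mutation status does not apply to a proportion, and no other between-group test for response rate is given

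*Combined protocol and SAP*

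**What the plan says.** Secondary objective 4 (section 2.1 and the Synopsis) is this: "To retrospectively explore the PFS and RR in patients based on RAS, BRAF, and PIK3CA mutation status". Synopsis, Statistical Methods item 2(d) describes it as "a separate analysis analyzing RR and PFS by RAS, BRAF, and PIK3CA mutation status to those without such mutations".

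The analysis is set out twice, in Synopsis item 5(d) and in section 8.1.2.4. Each place treats PFS and RR together. Each promises 95% confidence intervals per group and then says that "comparisons will be made using a stratified log-rank test". No strata are named.

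RR is defined in Synopsis item 2(a): "RR is defined using the RECIST 1.1 criteria as the proportion of subjects with a confirmed CR or confirmed PR". Section 8.1.2.1 uses the same definition. The only method given specifically for RR is in Synopsis item 5(a), repeated almost unchanged in section 8.1.2.1: "The point estimate of the RR with a 95% confidence interval based on the exact binomial distribution will be presented".

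**The concern.** A log-rank test compares distributions of time to an event. PFS, which runs from first dose to radiographic progression or death, is such a time. RR is a yes/no outcome per patient, summarised as a proportion. The plan therefore pairs one of its two endpoints with a test that cannot be computed for it, and offers no alternative.

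At stake is only the between-group RR comparison. Because the named test cannot be run, someone will have to pick another, possibly after seeing the response counts. With few responders, the usual candidate tests can disagree.

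There is also a minor wording point. Section 2.4 states: "This is an open-label, single-arm study which requires no blinding or randomization". There are thus no randomization strata for the word stratified to refer to. It may only mean grouped by mutation status, but the text does not say so.

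**Working it through.** **Step 1: match each endpoint to the named test.** The plan states no figure for this comparison, so there is none to reproduce.

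| Endpoint | Definition in the plan | Event time? | Log-rank test applies? |
|---|---|---|---|
| PFS | Section 8.1.1: time from first dose to radiographic progression or death | Yes | Yes |
| RR | Section 8.1.2.1: "the proportion of subjects with a confirmed CR or confirmed PR" | No | No |

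Time to response, which could in principle be given a log-rank test, is not defined anywhere.

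**Step 2: look for another RR comparison.** The exact binomial interval in Synopsis item 5(a) and section 8.1.2.1 is a one-sample estimate, not a comparison. Neither document part names a Fisher, chi-square, Cochran-Mantel-Haenszel, logistic or other method for two proportions.

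**Step 3: how small the groups could be.** Section 7.3 plans 16 patients in stage I and "an additional 28 subjects for stage II for a total of 44 subjects". The documents give no mutation frequencies, so the size m of the smaller group is an assumption. Expected responders in that group = m × overall RR, which reaches 5 when RR = 5/m. Five is a common rule of thumb for when a large-sample chi-square test is acceptable; it is not taken from the plan.

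| Assumed m | Overall RR needed for 5 expected responders |
|---|---|
| 22 (even split of 44) | 5/22 = 22.7%, i.e. 10 of 44 |
| 15 | 5/15 = 33.3% |
| 10 | 5/10 = 50.0% |

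With 9 responders among 44, an even split expects 22 × 9/44 = 4.5 per group. (The figure of 10 of 44 here counts responders; its match with the final 12-week PFS boundary is a coincidence.)

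**Step 4: whether the choice of test can matter.** Suppose 22 patients per group, with 4 responders in one and none in the other:

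- Fisher's exact test, two-sided: 2 × C(22,4)/C(44,4) = 2 × 7315/135751 = 0.108.
- Uncorrected chi-square: 44 × (4 × 22 − 0 × 18)² / (22 × 22 × 4 × 40) = 340736/77440 = 4.4, above the 5% critical value of 3.84.

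The same data are nominally significant by one test and not by the other. That is a reason to name the test in advance, and to name one suited to small counts.

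**The case against.** The strongest reply is that the sentence is merely compressed. A statistician would apply the log-rank test to PFS and report RR as proportions with intervals, and estimation without a p-value is acceptable for an exploratory aim. Item 2(d) is also loosely worded and does not explicitly call for a formal test of RR. This is a fair reading, and it lowers the stakes. It does not close the gap: the sentence on comparisons follows both endpoints, item 2(d) does set RR in mutated patients against RR in those without mutations, and on this reading RR has no comparison method at all.

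A second reply is that a late choice of test does little harm where no error rate or decision rule is attached. That stands, and it is why the point ranks low, although the objective is listed as secondary rather than exploratory.

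A third is that the arithmetic in Step 3 supports a particular replacement rather than measuring the fault. That is correct, and it is used only for that purpose. It is also a best case: 44 is the maximum, and the trial can stop after 16. Under the null 12-week rate of 13%, the probability of 2 or fewer successes in 16 is 0.654. Section 5.1.9 labels archival tissue optional although section 4.1 requires it, so fewer patients may be genotyped. Both considerations make the groups smaller.

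Finally, the mutation-status text does not name an interval method. Using exact binomial intervals per group extends what is specified for overall RR.

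**Conclusion.** The concern holds. For RR as defined, the one between-group test named does not apply, and no other is given, in either place where the analysis is described. The log-rank test remains valid for PFS.

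The consequence is small. Only the RR comparison by mutation status is affected. Sections 2.1 and 8.2.1 make the objective a retrospective exploration and genotyping subject to funding. The per-group estimates, the sample size and the two-stage decision on 12-week PFS do not change.

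That RR cannot be given a log-rank test follows from the definitions and needs no assumption. The case for an exact method rests on the assumed group sizes of 22, 15 and 10. The documents do not say whether the three genes are compared separately or pooled, so no count of comparisons is offered.

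**What to change.** In both Synopsis item 5(d) and section 8.1.2.4:

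1. Limit the log-rank test to PFS.
2. State that RR will be compared between patients with and without the mutation by a method suited to small groups. Fisher's exact test is one example; an exact confidence interval for the difference in proportions would also serve.
3. State that each group's RR is reported with an exact binomial 95% confidence interval, as already specified for overall RR.
4. Delete the word stratified for PFS, or name the strata. The marker being compared must not be one of them.

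The cost is about one sentence in each of two places. Data collection, sample size and the two-stage decision rule stay as they are.

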8.1.3 Exploratory Endpoint

8.1.3.1 Biomarker Analysis

Exploratory analysis of predictive and pharmacodynamic biomarkers will be performed by collecting pre- and post-treatment peripheral blood collection during pretreatment period and again on Cycle 3 Day 1 +/- 5 days. Samples will be archived for future investigation. See Appendix C for list of biomarkers.

8.2 Biomarker, Correlative, and Special Studies

8.2.1 Laboratory Correlative Studies

Whole blood samples will be obtained at Cycle 1 Day 1 (-7 day window) and on Cycle 3 Day 1 (+/- 5 days) from consenting patients, which will then be shipped and stored in a repository for future analysis at The University of Arizona. Pending funding availability, archival tumor specimens will be genotyped at The University of Arizona Genetics Core, a CLIA-certified clinical laboratory. Other biomarkers may be evaluated based on ongoing preclinical experiments as well as the scientific literature.

8.2.2 Archival Tumor Tissue

Pending funding availability, MET copy number analysis and expression will be assessed by fluorescent in situ hybridization (FISH) and immunohistochemistry (IHC), to explore association with likelihood of response and/or PFS at 12 weeks in patients with metastatic refractory colorectal cancer treated with cabozantinib. Other biomarkers may be evaluated based on ongoing preclinical experiments as well as the scientific literature.

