Cabozantinib (XL184) is a potent, orally-bioavailable small-molecule inhibitor of multiple receptor tyrosine kinases, which has demonstrated early evidence of activity in a variety of solid tumors. This agent is currently FDA-approved for treatment of medullary thyroid cancer and renal cell carcinoma. The principal targets of cabozantinib are proteins central to cancer cell growth and tumor angiogenesis: VEGFR2/KDR, MET, RET, AXL, TIE2, and KIT. It is thought that the concurrent inhibition of MET and VEGFR2 underlie the primary activity of cabozantinib seen in solid tumors, differing from the multi-kinase activity of regorafenib, which does not inhibit MET. Based on the theory that dual MET and VEGFR2 inhibition may work synergistically, cabozantinib demonstrated superior survival compared to everolimus in a recently published phase III clinical trial in patients with relapsed/refractory renal cell carcinoma.

Preclinical data has shown that cabozantinib exhibits growth inhibitory and anti-tumor effects in human CRC cell lines as well as in patient-derived tumor xenograft (PDX) mouse models, respectively. More recently, assessment of treatment effects of cabozantinib versus regorafenib in 10 human CRC tumor explants showed that cabozantinib had greater anti-tumor activity in 9 out of 10 explants. Analysis of tumor growth inhibition index (TGII) demonstrated that cabozantinib was significantly more effective than regorafenib at inhibiting tumor growth (average TGII 3.202 versus 48.48, respectively, $P = 0.007$). Importantly, MET inhibition may be the cause for this difference in efficacy as the HCT116 parental cell line was sensitive to both compounds; however, regorafenib was inactive in the MET kinase active isogenic cell line. These findings suggest that cabozantinib may fill an unmet need by providing a safe and effective treatment once standard of care options are no longer available for patients with metastatic CRC.

We hypothesize that cabozantinib, through dual inhibition of MET and VEGFR2, will lead to improved clinical activity in patients with metastatic CRC refractory to standard of care therapy.

OBJECTIVES

The objectives of this study are:

© 2017 AGICC/Criterion Inc.

Template Final Ver. 25OCT2017

Protocol 17CRC01/EXELIXIS IST56/Version 2.0 10/27/18

PROPRIETARY & CONFIDENTIAL

Primary Objective:

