8 OTHER ANALYSES

8.1 Analytic Plan Primary, Secondary, and Exploratory Endpoints

8.1.1 Primary Endpoint:

Progression-free survival will be defined as the time from administration of the initial dose of cabozantinib to evidence of radiographic progression as defined by RECIST criteria or death from any cause without evidence of disease progression, whichever occurs first. Each patient will be examined for PFS at 12 weeks and dichotomized as either having progression or not. Using an optimal Simon 2-stage design, the first 16 patients will be enrolled and 12-week PFS will be determined. If 3 or more of these patients have not progressed by 12 weeks, the trial will accrue an additional 28 patients for a total of 44 patients. If 10 or more (total) of these 44 patients are free of progression at 12 weeks then the Null Hypothesis will be rejected in favor of the alternative suggesting that the treatment has sufficient efficacy to warrant future study.

Kaplan-Meier estimates of PFS rates will be calculated along with their corresponding 95% confidence intervals.

Evaluable for Response

Only those participants who have received at least 2 cycles of therapy, and have had their disease re-evaluated will be considered evaluable for response. Note: Participants who exhibit objective disease progression or die prior to Cycle 3 will also be considered evaluable. Participants who do not meet the criteria for being evaluable for response defined above may be replaced to reach the sample size necessary for interim analysis.

8.1.2 Secondary Endpoints:

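### The exploratory MET analysis names only yes/no outcomes although PFS time is collected; under stated assumptions, using 12-week status alone costs roughly 7 to 20 points of power.

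*Combined protocol and SAP*

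**What the plan says.** Section 8.2.2 makes the FISH and IHC work on MET dependent on funding and gives its purpose as "to explore association with likelihood of response and/or PFS at 12 weeks in patients with metastatic refractory colorectal cancer treated with cabozantinib". The synopsis repeats this under Other Assessments. No test, MET cut-off, significance level or power is given.

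Section 8.1.1 fixes what PFS at 12 weeks means: "Each patient will be examined for PFS at 12 weeks and dichotomized as either having progression or not". It also defines PFS as a time ("Progression-free survival will be defined as the time from administration of the initial dose of cabozantinib") and adds that "Kaplan-Meier estimates of PFS rates will be calculated along with their corresponding 95% confidence intervals".

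For PFS and response by RAS, BRAF and PIK3CA status, Section 8.1.2.4 says that "comparisons will be made using a stratified log-rank test", and then that "Other biomarkers may be evaluated based on ongoing preclinical experiments as well as the scientific literature". It neither names nor excludes MET.

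The synopsis gives the reason for interest in MET: "We hypothesize that cabozantinib, through dual inhibition of MET and VEGFR2, will lead to improved clinical activity". Section 8.2.3 and Appendix C list blood markers of the MET/HGF and VEGF pathways as candidates for future or possible analysis.

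**The concern.** The 12-week cut discards information that the trial already holds. Scans are due at weeks 6 and 12 and then every 9 weeks (Section 5.5). Cut at 12 weeks, a progression found at week 6 counts the same as one found at week 12, and one at week 21 counts the same as one a year later.

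The Simon rule needs a yes/no count because it compares a number of patients with a threshold. The MET association feeds no stopping rule and no threshold, so that reason does not carry over.

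Numbers are small either way. At the plan's own rates the progression-free group would be 0.13 × 44 = 5.7 to 0.33 × 44 = 14.5, or about 6 to 15 patients. An association that exists is then easily missed, in a marker that the protocol's rationale puts at the centre.

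**Working it through.** **1. The plan's own figures.** These concern the primary endpoint; none is stated for MET. Continue with at least 3 of 16; reject the null with at least 10 of 44. P(reject) = Σ over x = 3 to 16 of P(X₁ = x) × P(X₂ ≥ 10 − x), with X₁ ~ Bin(16, p) and X₂ ~ Bin(28, p).
- p = 0.13: 0.0441 (stated 0.0441).
- p = 0.33: 0.9055 (stated 0.906).
- Expected N at p = 0.13: 16 + (1 − 0.654) × 28 = 25.69 (stated 25.7).

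The design reproduces, and nothing below alters it.

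**2. Inputs for the MET comparison.**
- From the documents: N = 44; 12-week PFS 33% (the alternative); the scan schedule; 79% MET overexpression in Section 1.3.1. The count given there, 236/286, is 82.5%.
- Assumed, because the documents are silent: hazard ratio (HR) 0.4 to 0.7 for MET-high against MET-low, a 50/50 or 79/21 split, exponential PFS, proportional hazards, two-sided 5%.

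**3. From HR to 12-week rates.** With a share q MET-high, S_high = S_low^HR and q·S_high + (1 − q)·S_low = 0.33. For q = 0.5 and HR 0.5, S_low = 0.206 and S_high = 0.454 (mean 0.33).

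**4. Power by formula, HR 0.5, 22 patients per group.**
- 12-week status: difference 0.248; null SE = √(2 × 0.33 × 0.67 / 22) = 0.142; alternative SE = √((0.206 × 0.794 + 0.454 × 0.546) / 22) = 0.137. Power = Φ((0.248 − 1.96 × 0.142) / 0.137), which is 41%.
- PFS time, 44 events (Schoenfeld): Φ(|ln 0.5| × √(44 × 0.5 × 0.5) − 1.96) = Φ(2.299 − 1.96) = 63%.

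The same formulas across HRs (50/50 split; losses taken before rounding):

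| HR | 12-week status | Log-rank, 44 events | Loss, 44 events | Loss, 36 events |
|---|---|---|---|---|
| 0.4 | 63% | 86% | 23 | 16 |
| 0.5 | 41% | 63% | 22 | 13 |
| 0.6 | 25% | 40% | 14 | 8 |
| 0.7 | 15% | 22% | 7 | 4 |

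For a 79/21 split with 44 events the formula losses are 34, 24, 14 and 7 points. The formula ignores that progression is dated only at scans, so it flatters the log-rank test, most of all with an uneven split.

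**5. Simulation with progression dated at the planned scans** (n = 44, 33% 12-week PFS, log-rank minus chi-square, in points):

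| HR | 50/50 split | 79/21 split |
|---|---|---|
| 0.4 | 17 | 20 to 21 |
| 0.5 | 17 to 18 | 15 |
| 0.6 | 11 to 12 | 9 to 11 |
| 0.7 | 6 to 8 | 5 |

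Ranges reflect simulation error between runs. At the 50/50 split the powers are about 57% against 40% at HR 0.5, 37% against 25% at HR 0.6 and 21% against 13% at HR 0.7. Against Fisher's exact test the losses are larger. For MET as a continuous score the picture is similar: Cox 69% against logistic 52% at HR 0.65 per SD, and 92% against 76% at HR 0.55 per SD.

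**6. Where the gain shrinks or disappears** (50/50 split, simulated).
- HR 0.5 with censoring after week 12 that leaves about 37 events: 50% against 39%.
- 30 assayed patients, HR 0.6: 25% against 19% to 22%.
- HR 0.5 up to week 12 and 1 afterwards: 39% against 41%, so no gain.

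**The case against.** The strongest reply is that the analysis is exploratory, depends on funding and commits to no test. Twelve-week PFS is the primary endpoint, and relating a marker to the primary endpoint is an ordinary choice. Section 8.1.2.4 leaves other biomarkers open, so a PFS-time analysis by MET is not ruled out. All of this stands and limits the weight of the point. It does not explain why Section 8.2.2 should name only the less informative form of an outcome held in full.

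Second, the gain depends on assumptions. Patients may stop treatment for toxicity or loss of clinical benefit (Section 2.6), and Table 5-1 marks no tumour assessment in the post-treatment column, so there may be fewer events than patients. Archival tissue is an inclusion requirement in Section 4.1 but headed optional in Section 5.1.9, so fewer than 44 may be assayed. Both objections stand, and step 6 shows their effect. At HR 0.6 or weaker, power is low whichever outcome is used, and a negative result would not count against MET.

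Third, a reader might infer that this is the trial's only planned test of its mechanism, and that the plan forfeits a fixed amount of power to confirm it. The documents support neither. No test is specified, and other MET/HGF and VEGF markers are listed. The synopsis hypothesis concerns improved clinical activity, which the Simon count addresses. In a single arm, no MET-outcome association separates prognosis from drug effect, and Section 1.3.1 itself reports that MET overexpression went with poor prognosis. Changing the outcome scale does not cure that.

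**Conclusion.** The point holds as a conditional loss of efficiency in an exploratory analysis. Section 8.2.2 names two yes/no outcomes for MET, while PFS time is collected and a log-rank comparison is planned for the mutation groups.

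With proportional hazards, exponential PFS, 33% 12-week PFS, n = 44 and two-sided 5%, the cost of using only 12-week status for a binary MET marker is roughly 7 to 20 points of power at HR 0.7 to 0.4. Single simulated settings run from 5 to 21. This is not a bound: the HR and the split are assumptions, heavier censoring or fewer assayed patients reduce the loss, and an effect confined to the first 12 weeks removes it. The primary analysis and its operating characteristics are unaffected.

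**What to change.** In Section 8.2.2 and the synopsis (Other Assessments), replace the outcome wording with text to this effect: The association of MET copy number and of MET expression score with PFS will be assessed on PFS time from first dose by Cox regression, with MET entered as a continuous or ordinal variable, and reported as a hazard ratio with 95% confidence interval. Twelve-week PFS status and confirmed response by MET will be reported alongside. Because the trial has a single arm, the result is exploratory and cannot separate a prognostic from a predictive effect.

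Leave the Simon 12-week count as it is.

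The cost is a short change of wording in two places, with no added patients, scans, samples or assays. The small downside is a proportional-hazards assumption in an exploratory model. The 12-week table shown beside it would help to reveal an effect limited to the early period.
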